2.6 PLANNED SAMPLE SIZE AND NUMBER OF STUDY CENTERS

Approximately 210 patients (~ 30 patients per age/dose group) will be recruited for this study at approximately 20 clinical sites in the United States. The patients will be enrolled in this multi-center outpatient study by physicians who -have been qualified as Investigators.

3. STUDY POPULATION

Patients must meet all of the inclusion criteria and none of the exclusion criteria listed below to be enrolled in the study.

3.1 INCLUSION CRITERIA

A patient will be eligible for study participation if he or she meets all of the following criteria:

1. Male or female child or adolescent age 6 to < 18;
2. Meets ROME IV criteria for child/adolescent IBS-C defined as:
For at least 2 months before diagnosis the patient has had:
 1. Abdominal pain at least 4 days per month associated with one or more of the following:
 - a. Related to defecation
 - b. A change in frequency of stool
 - c. A change in form (appearance) of stool;
 2. The pain does not resolve with resolution of the constipation (children in whom the pain resolves have functional constipation, not irritable bowel syndrome);
 3. After appropriate evaluation, the symptoms cannot be fully explained by another medical condition
 4. More than one-fourth (25%) of bowel movements with Bristol stool form types 1 or 2 and less than one-fourth (25%) of bowel movements with Bristol stool form types 6 or 7 on the BSFS or 4 or 5 on the mBSFS-C;
3. Patient's parent/guardian/LAR is able to voluntarily provide written, signed, and dated consent and patient is able to voluntarily provide assent as per IRB guidance;
4. Patient and patient's parent/guardian/LAR demonstrates an understanding, ability, and willingness to fully comply with protocol requirements and study procedures (e.g., acceptance of venipuncture, acceptance of urine drug screen for opiates, visit schedule, complete daily electronic diary reporting).

3.2 EXCLUSION CRITERIA

A patient will be excluded from the study if he or she meets any of the following criteria:

1. The patient has a mental age <4 years in the investigator's opinion;
2. The patient has previously been diagnosed with anorectal malformations, neurological deficits, or anatomical anomalies that would constitute a predisposition to constipation;
3. The patient currently requires iron supplements, amitriptyline, or other tricyclic antidepressants for depression, opioid-containing medications or compounds for pain, or has other conditions that require medications known to cause constipation. A patient with an onset of constipation prior to the use of these medications and who has been on a stable dose for at least 8 weeks prior to Screening might be considered eligible for this study if the investigator deems these medications do not significantly contribute to the patient's constipation. Screening of these patients needs to be approved by the medical monitor and the sponsor;
4. The patient is pregnant or lactating;
5. Females age 12 to < 18 or females age 6 to 11 of childbearing potential (defined as post menarche) who does not agree to practice one of the following medically acceptable methods of birth control throughout the study;
 - Hormonal methods such as oral, implantable, injectable, vaginal ring, or transdermal contraceptives for a minimum of 1 full cycle (based on the patient's usual menstrual cycle period) before study drug administration.
 - Total abstinence from sexual intercourse (since the last menses before study drug administration
 - Intrauterine device.
 - Double-barrier method (condoms, sponge, or diaphragm with spermicidal jellies or cream.

6. The patient follows a diet not considered normal by the investigator for the patient's age, relative to variety of food, caloric content, and quantity. The patient must have been on a stable diet for at least 30 days prior to Screening;
7. The patient's mobility or normal exercise tolerance is compromised in the investigator's opinion;
8. The patient has a history of an eating disorder;
9. The patient has clinical or laboratory signs and symptoms of significant cerebral, respiratory, renal, hepatobiliary, pancreatic, intestinal (including acute appendicitis, inflammatory bowel disease, or undiagnosed abdominal pain), endocrinologic, or infectious disease that in the investigator's judgment could interfere with study assessments or completion of the study. (Note: A patient with a history of thyroid disease may be enrolled if he or she has normal T3 and T4 at Screening. If the patient is taking medication for active thyroid disease, his or her T3 and T4 level must be within normal limits and the dose of any medication used to treat it must be stable for at least 30 days prior to Screening);
10. The patient has any other medical condition or is receiving concomitant medication or therapy that would in the investigator's opinion compromise his or her safety or compliance with the study protocol or compromise data collection;
11. The patient has a history or evidence of drug or alcohol abuse in the 12 months before Screening;
12. The patient has a hypersensitivity, allergy, or contraindication to plecanatide;
13. The patient has received any experimental drug, including linaclotide and lubiprostone, or experimental therapy within 30 days of study start;
14. The patient is unable to tolerate protocol-prescribed rescue medication (Dulcolax®), or unwilling to use it as the only laxative for the duration of the trial;
15. The patient has taken a medication considered to be a protocol-defined prohibited prior or concomitant medication or supplement as defined in section 3.3.2;
16. The patient and his or her caregiver are unable to communicate well with the study staff and comply with the study requirements (restrictions, appointments, and examination schedule). (The patient/caregiver must be able to complete required Daily BM and Symptom diary entries during the Screening/Baseline period and for the duration of the study. The patient/caregiver must also agree to provide contact information to receive daily reminders should the patient not complete the daily electronic diary entries or require password resets);
17. The patient has been screened for or participated in this or another Synergy study in the past;
18. The patient has a sibling that is currently participating or has participated in another Synergy study.

Exclusion Criteria Based on Baseline Diary Entries

19. Patient reports having more than 1 loose, mushy stool (Diary-recorded stool consistency of 6 on the Bristol Stool Form Scale (BSFS or 4 on the modified Bristol Stool Form Scale for Children [mBSFS-C]) or any watery stool (Diary-recorded stool consistency of 7 on the BSFS or 5 on the mBSFS-C) with any SBM that occurred in the absence of laxative use on the calendar day of the BM or the calendar day before the BM during each 7-day (week) period before the randomization day and up to the day of randomization;
20. ≥ 3 CSBMs per week for either week of the 2-week baseline diary assessment immediately preceding the randomization visit;
21. > 6 SBMs per week for either week of the 2-week baseline diary assessment immediately preceding the randomization visit;
22. Patient reports worst abdominal pain intensity (WAPI) scores in the 2-week baseline diary that meet either of the following:
 - a. WAPI score of 0 on the 11-point Numeric Rating Scale or Wong-Baker Faces® Pain Rating Scale for more than two days during each week of the 2-week baseline diary period.
 - b. An average WAPI < 3 for either of the two weeks of the baseline diary;

23. Completion of < 5 of the 7 required daily diary entries in each week of the 2-week baseline diary assessment immediately preceding the randomization visit;
24. Use of rescue medication (Dulcolax®, bisacodyl) for more than 2 days during either of the two weeks of the 2-week baseline diary assessment immediately preceding the randomization visit.

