	
groups. Patients will take their daily oral dose of the study drug once daily for 4 weeks and continue to complete their daily electronic diaries recording BMs, rescue medication use for constipation, and abdominal pain and other symptoms. At Weeks 1 and 4 of the Treatment Period, patients will return to the clinic to undergo safety and efficacy assessments.
 
Post-treatment Follow-up Period: For 2 weeks after the last dose of study drug, patients will continue to complete their daily electronic diaries. Patients will then return to the clinic for a final Follow-up visit at the end of Week 6.
 
The planned duration of participation in this study will be approximately 10 weeks from signing of informed consent/assent through post-treatment.

Study Drug	
Group A: Plecanatide 0.5 or 1.0 mg tablets and matching placebo for oral administration
 
Group B: Plecanatide 0.5, 1.0, or 1.5 mg tablets and matching placebo for oral administration

Treatment	
Following a 28-day Screening/Baseline Period, patients will take the assigned dose of study drug each morning at approximately the same time for 4 weeks. Dulcolax® will be provided as a rescue laxative that can be used if a patient has not had a bowel movement for at least 72 hours. Patients will be advised that it is preferred that they do NOT take rescue medication for the period from 24 hours before to 72 hours after Day 1 of dosing.

Number of Patients and Population	
Approximately 210 children with IBS-C will be randomized (~30 in each age/dose group) into the double-blind portion of the study. Eligibility for study enrollment (< 3 Complete Spontaneous Bowel Movements [CSBMs] for each baseline diary week, \leq 6 SBMs per week for each baseline diary week, a weekly average of abdominal pain score \geq 3 on an 11-point [0-10] Numerical Pain Rating Scale or Wong-Baker Faces® Pain Scale for each baseline diary week or \leq 2 days per week with abdominal pain score = 0 for each baseline diary week, \leq 1 day in each baseline diary week with BSFS = 6 for any SBM and no SBM with BSFS = 7 in either week for Group B or mBSFS-C = 4 for any SBM and no SBM with mBSFS-C = 5 in either week for Group A, adequate diary entry compliance, and proper use of rescue medication) will be confirmed by electronic diary entries made during each week of the two-week baseline diary assessment.

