***Soiling of underwear in younger children may be indicative of Fecal Incontinence**

To remain eligible for the study, patients must complete at least 5 of the 7 days of electronic End-of-Day diary entries for each of the 2 weeks of Baseline diary period.

Compliance with diary entries should be a focus for patient education at the telephone contact visits and as needed per the judgement of the clinical site staff.

The following endpoints will be assessed using data collected via the electronic diary in “real time”:

• *Frequency of Bowel Movements*

Patients/caregivers will be asked to report each BM experienced.

• *Stool Consistency*

Patients/caregivers will be asked to rate the patient’s stool consistency according to the BSFS (see **Appendix C**) or mBSFS-C (see **Appendix D**), which will be provided to them in the form of a laminated card (and will appear on the appropriate electronic device) at the Screening Visit (Visit 1), and may be referred to as often as necessary throughout the Screening, Treatment and Post-treatment Periods. The BSFS and mBSFS-C are validated measures of stool consistency commonly used in clinical trials.

• *Stool Diameter*

Patients/caregivers will be asked to report the number of large diameter stools. A large diameter stool is defined as one that is large enough to clog the toilet.

• *Use of Rescue Medication (RM)*

Patients/caregivers will report the use of provided rescue medication (Dulcolax®), including time of use and amount of rescue medication used. Use of rescue medication will determine whether a BM was spontaneous, but only this aspect of rescue medication use is part of the primary endpoint.

The following endpoints will be assessed using data collected via the electronic diary at the end of the day:

• *Fecal Incontinence*

As part of the daily diary (end of day), the following question will be asked:

How many episodes of fecal incontinence did you experience today?

0 1 2 3 more than 3

• *IBS Symptoms*

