8.4.1 Missing Data Conventions

Missing values of safety parameters will not be imputed.

The weekly BM (SBM, CSBM) rate is the sum of the BMs (SBMs, CSBMs) recorded for the days in the week for which a BM response is recorded in the daily diary. Note that this is equivalent to a “worst case” analysis in that the BM (SBM, CSBM) rate for the week is the sum of the BMs (SBMs, CSBMs) recorded for the days in the week for which BMs were reported, plus 0 BMs (SBMs, CSBMs) for each day in the week for which the BM response is missing. In any week in which no BM response is recorded, the weekly BM (SBM, CSBM) rate will be set to 0 in any summary or linear mixed-effects model analysis involving

the weekly BM (SBM, CSBM) rate. In particular, for a randomized patient who withdraws from study participation prior to the end of the study, the patient is considered to have a weekly BM (SBM, CSBM) rate equal to 0 for any weeks remaining in the planned duration of the study for which the patient has no BM responses recorded.

The weekly average IBS-related daily abdominal pain score is the average of the non-missing, abdominal pain scores recorded in that week, i.e., the weekly average is the sum of the abdominal pain scores recorded in the diary in the given week, divided by the number of pain scores recorded in the week. In any week in which a patient has no diary days for which an abdominal pain score is recorded, the weekly average abdominal pain score will be set to missing. In any linear mixed-effects model analysis involving the weekly average abdominal pain score, if the average score is set to missing in a given week, it will be left as missing in the linear model. In particular, for a randomized patient who withdraws from study participation prior to the end of the study, the weekly average abdominal pain score will be set to missing for any weeks remaining in the planned duration of the study for which the patient has no abdominal pain data.

In any analysis of the frequency of fecal incontinence, the frequency of defecation pain, and the frequency of large diameter stools will follow the same methodology as described above for the determination and analysis of the weekly BM rate.

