8.4.3 Baseline Definition

For each safety parameter, the most recent valid assessment recorded before randomization will be used as the baseline for all analyses of that safety parameter.

For efficacy parameters, the baseline values will be derived from data collected in the 2-week electronic diary assessment at the end of the Screening Period (baseline). The last 14 days of diary entries prior to Day 1 will be the default standard for derivation of these values.

The baseline BM (SBM, CSBM) weekly rate will be the weekly average number of BMs (SBMs, CSBMs) recorded during the 2-week baseline assessment period; similarly, for frequency of abdominal pain and abdominal discomfort, frequency of fecal incontinence, frequency of defecation pain, and frequency of large diameter stools. Baseline stool consistency, severity of abdominal pain, abdominal discomfort, and severity of defecation pain will be calculated as follows: for each week of the baseline assessment, the weekly average is the sum of the non-missing scores recorded during the week divided by the total number of non-missing scores recorded during that week; the baseline is then equal to one-half of the sum of the two weekly average scores.

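### Exclusion 23, read literally, removes only patients with sparse diaries in both baseline weeks, which conflicts with Section 4.2.1; correct the wording and confirm which rule the IWRS applies

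*Combined protocol and SAP*

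**What the plan says.** **The entry gate.** Protocol Section 3 states: "Patients must meet all of the inclusion criteria and none of the exclusion criteria listed below to be enrolled in the study". Item 23 in Section 3.2 excludes for "Completion of < 5 of the 7 required daily diary entries in each week of the 2-week baseline diary assessment".

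**Its neighbours.** Item 20 excludes for "≥ 3 CSBMs per week for either week of the 2-week baseline diary assessment". Item 24 excludes for rescue use "for more than 2 days during either of the two weeks of the 2-week baseline diary assessment". Items 21 and 22b also say *either*; items 19 and 22a say *each*.

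**The conflicting rule.** Section 4.2.1, on remaining eligible, says "patients must complete at least 5 of the 7 days of electronic End-of-Day diary entries for each of the 2 weeks" of the baseline diary period.

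**The other places that mention compliance give no number.** The synopsis says that "adequate diary entry compliance, and proper use of rescue medication) will be confirmed by electronic diary entries made during each week" of the two-week baseline. Section 5.2.2 has the IWRS generate diary eligibility from the previous 14 days, restricts it to patients who showed diary and rescue compliance, and takes the evaluation of diary data out of the site's hands. Note h to the Schedule of Assessments confirms that the review is programmatic.

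**How missing days reach the baseline.** Protocol Section 8.4.1 sums recorded movements, "plus 0 BMs (SBMs, CSBMs) for each day in the week for which the BM response is missing". SAP Section 3.3.4 does the same and sets a week with no response to 0. The baseline rate in Protocol Section 8.4.3 is "the weekly average number of BMs (SBMs, CSBMs) recorded during the 2-week baseline assessment period". SAP Section 5.2.2 agrees. Neither sets a minimum number of diary days or scales to days observed.

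**The concern.** An exclusion that fires when a shortfall occurs in each of two weeks is met, on a literal reading, only when both weeks fall short. A requirement to reach a threshold in each of two weeks is failed when either falls short. The two sentences look alike but give different rules, and the word *each* produces the looser one in the exclusion list. Since a program decides diary eligibility, a specification written from the numbered criteria could carry the looser rule without anyone at the site noticing.

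The primary endpoint is change from the diary baseline, and that baseline is also a covariate in the primary model. If days without a response are scored as zero, a sparse baseline week lowers the baseline, and the patient may appear to improve without any change in bowel habit. Unrecorded days also make the CSBM, SBM and rescue limits in items 20, 21 and 24 easier to pass, so those items would not reliably catch such a patient.

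**Working it through.** The plan gives no figure that depends on item 23, so there is none to reproduce. The check compares the two rules and then traces the effect on the baseline.

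**Step 1: the two rules.** Let a and b be the completed days (0 to 7) in baseline weeks 1 and 2, giving 8 × 8 = 64 patterns.

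- Literal item 23 excludes if a < 5 and b < 5. That is 5 × 5 = 25 patterns, so 64 − 25 = 39 pass.
- Section 4.2.1 requires a ≥ 5 and b ≥ 5. That is 3 × 3 = 9 patterns.

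The rules disagree on 39 − 9 = 30 patterns. These are counts of possible patterns, not of patients. The fewest completed days that pass are 5 of 14 (5+0) under literal item 23 and 10 of 14 (5+5) under 4.2.1. The largest share of baseline days that could be missing is 9/14 = 64% and 4/14 = 29% respectively.

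**Step 2: effect on the baseline.** Let r be the true weekly SBM rate. The documents give no baseline rate, so r = 1 to 6 is an assumption; item 21 caps recorded SBMs at 6 per week. Assume also that:

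- SBMs are spread evenly over days;
- no bowel movement is recorded on a day without a completed entry;
- the patient's true rate does not change;
- the diary is complete after randomization.

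Then:

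- derived baseline = r × (a + b)/14
- artificial change = r − baseline = r × (14 − a − b)/14

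| Days completed | Passes literal item 23 | Passes 4.2.1 | Baseline at r = 3 | Artificial change at r = 3 | Range, r = 1 to 6 |
|---|---|---|---|---|---|
| 7+7 | yes | yes | 3.00 | 0 | 0 |
| 5+5 | yes | yes | 2.14 | +0.86 | +0.29 to +1.71 |
| 7+1 | yes | no | 1.71 | +1.29 | +0.43 to +2.57 |
| 7+0 | yes | no | 1.50 | +1.50 | +0.5 to +3.0 |
| 5+0 | yes | no | 1.07 | +1.93 | +0.64 to +3.86 |

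For example, 7+0 at r = 3 gives 3 × 7/14 = 1.50, and 3 − 1.50 = 1.50. Each entry is an upper bound for its pattern, because any movement recorded on a day without a completed entry raises the baseline.

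**Step 3: would rescaling the baseline help?** Take an unchanged patient at an assumed 4 SBM per week with 5 of 7 days recorded in every week.

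- Current rule: baseline 4 × 5/7 = 2.86, treatment weeks 4 × 5/7 = 2.86, change 0.
- Baseline rescaled to recorded days, treatment weeks left as they are: baseline 4.0, treatment 2.86, change 2.86 − 4.0 = −1.14.

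Rescaling one side only creates an error that the present symmetric rule avoids.

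**The case against.** The strongest reply is that the protocol already bars these patients. Section 4.2.1 is itself an eligibility rule, the synopsis lists diary non-compliance as a key exclusion, and Section 5.2.2 admits only diary-compliant patients. A sparse week enters only if the IWRS follows item 23 literally and ignores 4.2.1, and the documents do not show the algorithm. This stands, and it makes the consequence conditional. It does not remove the conflict, because only 4.2.1 gives a number that contradicts item 23, and it lies outside the lists that Section 3 makes the gate.

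A reader might infer from *either* in items 20, 21, 22b and 24 that item 23 deliberately sets a both-weeks rule. The documents do not support that. Items 19 and 22a also say *each*, where the synopsis states the matching limits as conditions for every baseline week. That pattern, with 4.2.1, points to a drafting slip.

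The size is also open to challenge, with reason. Section 4.2.1 counts End-of-Day entries, whereas bowel movements are also reported episodically as they occur, so a week short of End-of-Day entries may still hold bowel movement records. Missing treatment days are scored zero too, so continued poor compliance would offset the artefact. A wholly empty week leaves the average pain score in item 22b undefined and might be caught, depending on coding; weeks with one to four entries are the clearer risk. Nothing indicates how many patients would be affected.

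Finally, a reader might set the artificial change beside the planned difference of 1.5 in Protocol Section 8.2 and infer a threat to the treatment effect. That comparison does not hold. The 1.5 is a difference between arms, while the artefact is a change within one patient. Baseline compliance precedes randomization, so the arms are affected alike in expectation.

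**Conclusion.** The contradiction is real. Item 23 as worded and Section 4.2.1 give different answers for any patient with one adequate and one inadequate baseline week, and 4.2.1 shows the likely intent. What follows is conditional on the IWRS being programmed to literal item 23, which the documents neither show nor rule out.

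If it is, the minimum baseline falls from 10 to 5 completed days of 14. For a 7+0 pattern, the artificial change is at most +0.5 to +3.0 SBM per week over assumed true rates of 1 to 6, given no bowel movement records on missing days and a complete diary after randomization. The cost is noise in the baseline covariate, inflated within-arm change and some patients of doubtful eligibility. The contrast with placebo is not biased in expectation. The correction is worth making because it is small and concerns an operative entry criterion.

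**What to change.** 1. In item 23, replace *in each week* with *in either week* of the two-week baseline diary assessment.
2. Align the entry type: item 23 refers to daily diary entries, Section 4.2.1 to End-of-Day entries. Use End-of-Day in both.
3. Confirm that the IWRS diary-eligibility algorithm applies the corrected rule. If randomization has begun, count the randomized patients with fewer than 5 End-of-Day entries in either baseline week; this would show whether the problem arose in practice.

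Do not rescale the baseline alone to recorded days. Treatment weeks would stay unscaled and the change score would become asymmetric. Up to 4 of 14 baseline days can still be scored as zero after the correction, so the plan should say plainly that this is intended and that the same rule applies before and after randomization.

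The cost is a one-word correction, an aligned term and a specification check, with possibly a few more screen failures, all of whom Section 4.2.1 already bars.
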